7. RESEARCH PLAN

7.1 Selection of Subjects

7.1.1. Subject Population.

Patients ages 18 and older presenting to the Emergency department with a complaint of nausea and/or vomiting. All presumed causes of nausea will be included. Inclusion/exclusion criterion is based on safety considerations that were discussed with SAMMC clinical pharmacist. Other considerations are circumstances that altered smell or perception, exogenous emetics, concomitant antiemetic therapy and alcohol exposure. No specimens will be obtained.

7.1.2. Source of Research Material.

Source of Research Material	Conducted for Clinical Purposes(Y/N)	Conducted for Research Purposes
VAS Nausea Score	N	Y
Case Report Form	N	Y

VAS Patient Satisfaction Survey	N	Y
CHCS ad hoc data for all ED patients with nausea or vomiting including those not enrolled in the study for purpose of ruling out selection bias in study population	N	Y

34
 35 **7.1.3. Inclusion and Exclusion Criteria.**

36 Inclusion Criteria:

- 37 (a) ages 18 and older
- 38 (b) complaint of nausea and/or vomiting reported at 3 or above on VRNS at the time of ED triage

39
 70 Exclusion Criteria:

- 71 (a) allergy to isopropyl alcohol or ondansetron
- 72 (b) inability to breathe through nose (e.g., recent upper respiratory infection)
- 73 (c) intake of cefoperazone, disulfiram, or metronidazole within the last 24 hours
- 74 (d) mental status precluding informed consent including intoxication
- 75 (e) known QT-prolongation
- 76 (f) clinical suspicion for serotonin syndrome
- 77 (g) intravenous catheter in place prior to study start
- 78 (h) medications administered since patient arrival to ED (e.g., in triage)
- 79 (i) suspected or known pregnancy

30
 31 **7.1.4. Description of the Recruitment and Prescreening Process.** ED providers and RN triage nursing staff (none of
 32 whom will be study team members) will be apprised of the study inclusion criteria to notify study team members of potential
 33 subjects. Potential subjects will be asked to quantify their nausea on a VNRS (0-10) for the purposes of discerning study
 34 eligibility by triage nurses, the RNs assigned to the patient, or the patient's provider. Efforts will be made to perform this
 35 prescreening process early in the patient's ED course (ideally at the time of triage or initial arrival to treatment room). No
 36 other history, physical exam or other evaluations beyond those normally conducted as the standard of care shall be performed

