 37 for the purposes of screening. Triage nurses, the RNs assigned to the patient, the provider assigned will, through their
 38 standard of care assessments and VNRS ascertainment, be able to identify potential subjects (those who meet inclusion
 39 criteria). Triage nurses will notify research staff of potential patients for study enrollment.

30
 31 **7.1.5. Consent Process.** Either the PI or one of the AIs will conduct the informed consent process, which will be
 32 accomplished in the ED while the patient is not receiving active-intervention. The process will take place with the curtain
 33 drawn or door closed to provide the subject appropriate privacy. The subject will have ample opportunity to ask questions of
 34 the investigators and to look over the consent form and HIPAA authorization. The subject will be offered the option of having
 35 a family member present and to be allowed the option of deferring a decision until later into their ED stay. Subjects unable to
 36 provide informed consent for themselves due to diminished decision-making capacity are excluded per paragraph 7.1.3. The
 37 informed consent will notify patients that they will be receiving one of two oral solutions and one of two preparation pads being
 38 studied for the treatment of nausea. They will not be informed of the identity of the substances or that one of the substances
 39 is inert (placebo) given that it is impossible to blind to smell hence we believe that effective blinding to the preparation pad
 40 contents would be impossible without withholding this information. Given the safety profile of these medications, we believe
 41 this research will pose no greater than minimal risk to the participants.

32
 33
 34 **7.1.6. Subject Screening Procedures.** Subjects will be recruited exclusively by the study investigators. Investigators will
 35 approach eligible subjects as identified by either the triage nurse, treating nurses, or treating providers. The recruiting
 36 investigator will inquire as to whether the patient is amenable to possible participation in a study of nausea treatments. If the
 37 patient agrees, the investigator will then verify the potential subject meets inclusion criteria without exclusion through subject
 38 self-report. Agreeable patients will undergo a complete, informed consent process. Data regarding potential subject's age,

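### Exclusions are verified by self-report only, which cannot establish exclusion (f) and can miss (e) and (h)

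*Combined protocol and SAP*

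**What the plan says.** Section 7.1.6 (Subject Screening Procedures) states how eligibility is verified: if the "patient agrees, the investigator will then verify the potential subject meets inclusion criteria without exclusion through subject", and the sentence ends on the next line, "self-report. Agreeable patients will undergo a complete, informed consent process". Self-report is the only source named.

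The exclusions in 7.1.3 that matter here are:

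- "e) known QT-prolongation"
- "f) clinical suspicion for serotonin syndrome"
- "h) medications administered since patient arrival to ED (e.g., in triage"

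Section 7.1.4 has nurses and providers, who are not study team members, identify candidates during usual care. They are told the inclusion criteria; the exclusions are not mentioned. The same section rules out any screening evaluation beyond standard care. Section 7.1.5 has an investigator conduct consent and refers back to 7.1.3 for patients who lack decision-making capacity. Section 7.3 goes from inclusion criteria and consent to baseline scores and dosing.

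**The concern.** Section 7.1.1 describes the criteria as resting on safety considerations discussed with a pharmacist, and 8.1 relies on an exclusion to limit reactions to inhaled alcohol. The uncommon reactions listed in 9.1 include QT prolongation and serotonin syndrome, the subjects of (e) and (f). A safety exclusion protects only if someone able to judge it is asked. Under 7.1.6 the only person asked is the patient, whom the protocol deliberately does not tell which substances are being tested (7.1.5 and 7.3). That patient has less reason to volunteer a relevant history.

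Exclusion (h) also has a statistical role. Section 7.2.1 says ondansetron is part of this ED's triage protocols, so a dose before enrolment is a realistic event. If it is missed, the patient's baseline and 30-minute VAS, the latter being the primary outcome, partly reflect a drug that the trial did not assign.

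**Working it through.** No figure in the plan bears on this point, so the check sets the passages side by side.

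**Step 1. Can the patient report each exclusion in 7.1.3, and does another stated step cover it?**

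| Exclusion | Can the patient report it? | Other stated check |
|---|---|---|
| (a) allergy | Yes | Not needed |
| (b) cannot breathe through nose | Yes | Not needed |
| (c) listed drugs in past 24 hours | Largely | None stated |
| (d) mental status, intoxication | Poorly | Investigator-led consent, 7.1.5 |
| (e) known QT prolongation | In part: it may be known only to the record | None stated |
| (f) suspicion of serotonin syndrome | No: it is a clinician's judgement | None stated |
| (g) intravenous catheter | Yes, and visible | Not needed |
| (h) drugs since ED arrival | In part: a chart fact | None stated |
| (i) pregnancy | Largely | None stated |

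The count is one that cannot be self-reported (f), two that can be in part (e, h), one covered at consent (d), one visible (g) and four that are largely the patient's own knowledge (a, b, c, i): 1 + 2 + 1 + 1 + 4 = 9.

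**Step 2. Does an earlier step fill the gap?** Staff in the referral path may hold the knowledge behind (e), (f) and (h), but 7.1.4 briefs them on inclusion only and asks them to identify patients who meet the inclusion criteria. Section 6 also has investigators approach patients at triage or in the waiting room. A treating provider may not yet have seen the patient, so no suspicion under (f) may have been formed.

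**Step 3. Does a later step fill it?** Under Section 6 a study team member enters the order and the ED pharmacy dispenses by study number. No eligibility check is described at either step.

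**Step 4. Size.** The documents give neither the prevalence of these exclusions nor the accuracy of self-report. Purely as an illustration, assume a share *p* of otherwise suitable patients meets one of them and screening detects a share *s* of those. Among *N* = 180 enrolled (7.4.1), the expected number wrongly enrolled is

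N × p(1 − s) / [p(1 − s) + (1 − p)].

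- *p* = 0.005, *s* = 0.95: 180 × 0.00025 / 0.99525 = 0.05
- *p* = 0.02, *s* = 0.80: 180 × 0.004 / 0.984 = 0.73
- *p* = 0.05, *s* = 0.50: 180 × 0.025 / 0.975 = 4.6

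These assumptions span practically none to about five patients. Both inputs are assumed, so this range is not an estimate.

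**The case against.** The strongest reply is that little is left once the criteria are read closely. Several parts of it stand.

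- A reader might infer that exclusion "d) mental status precluding informed consent including intoxication" is in the same position as (f). The documents do not support that: under 7.1.5 an investigator deals with the patient directly at consent, and patients without capacity are excluded there. It is not part of the gap.
- The word known narrows (e), and asking the patient is a reasonable first step. This stands, but the text does not say known to whom, so the gap for (e) is partial.
- Clinicians are in the referral path and may informally hold back a patient they suspect under (f). They may, but the text neither asks them to nor tells them the exclusion exists.
- Sections 7.3.2 and 7.7 collect history, medications, allergies and other information relevant to the criteria. This is described as data collection, not as an eligibility check, and 7.3.2 takes the history from the patient. The screening forms are not in the documents, so a line for each exclusion may already exist; 7.1.6 would still make self-report its source.
- Section 7.1.4 bars extra screening evaluations, and record review before consent could raise a HIPAA question, because the waiver in Section 6 is described only for the chart-review portion. Both points are met by asking the provider already treating the patient and consulting the existing record after consent.

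A reader might also infer harm from the fact that two of three arms receive ondansetron. Two thirds is only the expected allocation share of an unknown, possibly zero, number of patients. Section 7.2.1 describes the study dose as routine in this ED, so extra exposure over usual care is not shown.

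**Conclusion.** The point holds for three exclusions. As written, (f) cannot be applied through the stated method, and (e) and (h) can be missed by it. A patient meeting any of them could be enrolled and given study drug. The documents do not show that this would happen often, or that anyone would be harmed.

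For the analysis, a missed (h) could shift individual baseline and 30-minute scores. Screening precedes a blinded, randomised assignment, so I would expect such cases to fall across arms by chance and blur the comparison, not favour one arm systematically.

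The conclusion assumes that 7.1.6 means what it says and that no form or site procedure outside the documents supplies another source. It is a cheap improvement worth making, not a defect that undermines the trial.

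**What to change.** Reconcile 7.1.6 with 7.1.3 and 7.1.4:

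1. In 7.1.6, name the verification source for each exclusion: self-report, the treating provider, the existing record, or the investigator at consent.
2. For (e), (f) and (h), have the investigator confirm with the treating provider and the existing record after consent and HIPAA authorization and before the study drug order is entered. Record this on the screening form if no such line exists.
3. In 7.1.4, give referring staff the exclusion criteria along with the inclusion criteria.

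No criterion, test or clinical rule changes, and no staff are added. Section 7.3.2 already draws some study data from the ED record. The cost is protocol wording, perhaps one form line, a minute or two per patient, and possibly a few more screen failures after consent, which should be logged.

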22 NDC 0264-2101-00

23
24 We will be requesting an investigational drug exemption for the isopropyl alcohol pads IAW 32 CFR 312.2 for the following
25 reasons. We have no intentions of utilizing the results of this study to seek a new indication for the use of isopropyl
26 alcohol or to otherwise support any significant changes in the labeling of this product. Similarly, we have no intentions of
27 using the results of this study to support a significant change in the advertising of this product. Our route of administration
28 of this product will not significantly increase the risks associated with its use.

29
30 We will also be requesting an investigational drug exemption for the Ondansetron IAW 32 CFR 312.2 for the following
31 reasons. We have no intentions of using the results of this study to seek a new indication for use of ondansetron or to
32 otherwise support any significant changes in its labeling. Similarly, we have no intentions of using the results of this study
33 to support a significant change in the advertising of this medication. Our routes of administration of this medication will
34 not significantly increase the risks associated with its use.

35 Both the saline and isopropyl alcohol pads are lawfully marketed over the counter products and meet the conditions of
36 being generally safe and effective by the U.S. FDA due to their active ingredients and labeling. We consider the use of
37 the ISO (administered via the pad) as a drug in this research which meets the IND exemption criteria as outlined above.

38
39 Specifically regarding ondansetron, we will be using the conventional dose (4 mg) and route of administration for
40 ondansetron. While the patient population in this study (all patients with undifferentiated nausea and vomiting) differs
41 from that for which this medication is approved (chemotherapy patients), this agent has been extensively studied at this
42 dose in ED patient population without safety concerns.¹⁵⁻¹⁷ Moreover, this medication is routinely used at this dose in our
43 Emergency Department for the purpose of treating nausea and is incorporated into our triage protocols. Finally, this
44 investigation will be conducted in compliance with the requirements for IRB review and obtaining informed consent.

45
46 **7.2.2 Devices.** Not applicable.

47
48 **7.3. Study Procedures/Research Interventions.** Upon presenting to ED, meeting inclusion criteria and obtaining
49 consent, the subject's nausea and pain levels will be recorded initially. For the oral solution, they will be instructed to
50 swallow the oral solution. Receipt of oral solution (ondansetron or placebo) should occur prior to pad inhalation to be
51 followed within 5 minutes by initiation of inhalations from the allocated study pad (normal saline or ISO). For the
52 preparation pads, patients will be instructed to hold the pad approximately 1 inch from their nares and take deep nasal
53 inhalations as needed for nausea relief. Initiation of inhalations will mark time 0 for the study. If a subject is unable to or
54 prefers assistance with either nasal inhalation or oral solution consumption, the patient's nurse will provide any assistance
55 needed. The investigator will remain at arm's length from the patient at all times to avoid detecting prep pad scent.
56 Additionally, investigators will also instruct subjects to avoid any behavior or actions during the study that would indicate
57 which intervention is being used. Examples of behavior to avoid would be verbally describing the scent of the preparation
58 pad or taste of the oral solution. Investigators will not inform subjects which substances are being tested. The
59 preparation pads are commercially prepared single-use pads of ISO for the ISO + oral placebo and the ISO + oral
60 ondansetron study groups and commercially prepared single-use saline pads for the inhaled saline + ondansetron oral
61 solution group that are identical with the exception of the labeling. Both pads will remain in their original packaging. Pain
62 and nausea measurements will be gathered at 0, 10, 20, 30, and 60 minutes and then again hourly up to 5 hours, and
63 then finally at the time the patient's attending physician makes a disposition decision. The patient may withdraw from the
64 study at any time. At any time during the study, a rescue antiemetic drug can be considered by subject request or
65 provider preference. The individual pads will be de-identified, utilizing brown tape over original packaging that tears open

70 with packing as not to reveal manufacturer's labeling. The oral solution packaging will similarly be de-identified. The only
71 scenarios in which a study team member will prompt a provider to consider a rescue anti-emetic is if the patient vomits or
72 if the patient actively requests an alternative medication. A study data form will be completed for each subject by the
73 study investigators and secured daily in a locked cabinet, along with locked study file box, in the EM APD-R office.

74
75

Assessment	Visit / Follow Up (F/U) Interval Times					
	Initial Presentation	0 min (patient drinks oral solution and starts inhalations)	q10 min until 30 min	1 hour	Hourly until 5 hours	Disposition decision made by patient's attending physician
Study period/interval						
Screening	x					
Informed Consent, discuss Plan, etc.	x					
Allocation according to pre-generated simple randomization sequence	x					
Demographics, History of Present Illness	x					
Medication use	x					
Preparation pad provided		x				
Additional preparation pad offered if needed (up to 10)			x	x	x	
Oral solution provided		x				
Provider contacted for consideration of rescue anti-emetic if vomiting or if subject requests			x	x	x	
Nausea Vomiting VAS		x	x	x	x	x
Episodes of Vomiting		x	x	x	x	x
Pain VAS		x	x	x	x	x
Use of Antiemetic Medication		x	x	x	x	x
Type/Doses of fluids/medications		x	x	x	x	x
Clinical impression						x
Overall Satisfaction VAS						x
Pt perception of pad contents						x
Pt perception of oral solution contents						x
Provider perception of pad contents						x
Provider perception of oral solution contents						x
Investigator perception of pad contents						x
Investigator perception of oral solution contents						x
Summary of adverse events						x

76
77
78
79
30
31

This study concludes at the time of disposition and patient satisfaction will be solicited regardless of outcome.

7.3.1 Collection of Human Biological Specimens. Not applicable.

7.3.1.1 Laboratory evaluations and special precautions. Not applicable.

32
33 **7.3.1.2 Specimen storage.** Not applicable.
34

35 **7.3.2 Data Collection.**

- 36 -Times of subject arrival to ED, bed arrival, study medication receipt (gathered prospectively from order sheet or Essentris)
37 -Patient initial nausea as measured by screening VNRS (0-10): self-reported by the subject.
38 -Demographics: Age in years, sex, FMP/SSN, DOB will be recorded on the study key. Age in years and sex will also be
39 reported on the case report form (CRF). This information will be obtained from the patient's ED medical record labels.
40 -The patient's estimated height, weight, race, smoking history, alcohol use will be recorded on the CRF as self-reported by the
41 patient.
42 -History of Present Illness- Nausea and/or vomiting symptoms of timing, duration, severity, provocation and palliation along
43 with any other symptoms (i.e. pain) will be recorded on the CRF. This information will be self-reported by the subject.
44 -Pertinent Personal Medical/Surgical History will be recorded on the CRF. This information will be self-reported by the
45 subject.
46 -Current medications, supplements being taken and any allergies will be recorded on the CRF.
47 -Level of nausea, episodes of vomiting, pain level, adverse events, use of antiemetic medication at the 0, 10, 20, 30, and 60
48 minutes, then hourly up to 5 hours and finally at the time of patient disposition will be recorded on the CRF. Satisfaction level
49 will be recorded at study conclusion (time of patient disposition) on a VAS. This information will be self-reported by the
50 subject.
51 -Numbers of episodes of vomiting (discrete episodes separated by 120 seconds) will be recorded on the CRF as reported by
52 the patient or the patient's treating nurse.
53 -Time and doses for all drugs and fluids administered in the ED will be recorded on the CRF.
54 -Clinical impression at the time of patient disposition decision will be recorded on the CRF.
55 -Time of patient disposition decision made by attending physician will be recorded on the CRF.
56 -Any adverse events will be recorded on the CRF.
57 -Patient, provider, and study investigator perceptions of pad and oral solution contents will be recorded on the CRF.

58
59 **7.3.3. Human Biological Specimens/Tissue/Data Banking.** Not applicable.
60

61 **7.4 Statistical Consideration**

62
63 **7.4.1 Sample Size Estimation.**

64 **We expect the standard deviation of the change in baseline to 30 minute VAS scores to be approximately 28.7.¹⁷ We**
65 **define a clinically significant difference as 20 mm on the VAS.¹⁸ Given alpha = 0.025 (reflecting a Bonferonni**
66 **correction for testing of two hypotheses) and beta = 0.2 with two-tailed testing, we estimate we will require 40**
67 **patients per arm.**
68

Estimate Required Sample Size	120
Estimate Participant Drop Out / Withdrawal	60
Total Enrollment Requirement	180

69

Enrollment at Each Site	
SAMMC	180

70
71 **7.4.2 Primary (i.e., primary outcome variables) and secondary endpoints.** Primary outcome is nausea VAS measurement
72 at 30 minutes. Secondary outcomes include nausea VAS measurement at study disposition (the time at which the patient
73 leaves the ED), receipt of rescue anti-emetics, time to disposition, and patient satisfaction.
74

75 **7.4.3 Data analysis.** In this study, the primary outcome will be evaluated using a two-tailed independent sample student t test.
76 The primary outcome will further be evaluated using a multiple regression model. For secondary outcomes, scale data will be
77 compared using a two-tailed independent sample student t test while categorical data will be compared using a chi-squared
78 test.
79

80 **7.7 Confidentiality.**

31 Protection of Data. Subjects will be assigned a study number upon enrollment in order to facilitate subsequent removal of
32 identifiers upon completion of data analysis. The study number will be recorded on the data collection form and on a study
33 key, which links the study number with the subject's name, FMP, SSN, and DOB. Otherwise patients will be de-identified by
34 eliminating names and collecting only demographic (with ages greater than 89 categorized as "greater than 89"), general
35 description of chief complaint, personal medical, surgical, and medication history; and any other information specific to
36 inclusion and exclusion criteria. The case report forms, signed consent forms, and signed HIPAA authorizations will be stored
37 in a locked cabinet only accessible to the study investigators within the secure EM APD-R office.

38
39 **7.7.1 Certificate of Confidentiality.** N/A.

40 41 **8.0 RISKS/BENEFITS ASSESSMENT**

42
43 **8.1 Risks.** There is a risk to the subjects related to loss of confidentiality. However, this risk is minimized by using a
44 unique study code while collecting study data and limiting access to subject records to the study team. Since all patients
45 will be receiving treatment for nausea (either inhaled isopropyl alcohol, oral ondansetron, or both), we believe the risks of
46 delay in treatment or symptom relief are minimal. Nevertheless, if the treatment to which subjects are allocated is not
47 effective in treating their symptoms, they may experience a delay in rescue therapy and so a delay in symptom relief. We
48 seek to minimize this risk by permitting, subjects to request an antiemetic at any time and to withdraw from the study at
49 any time.

50
51 Additionally, there may be an extremely rare incident of a subject that may have a sensitivity to inhaling ISO. The
52 exclusion criteria were defined to minimize the risks of such reactions by excluding patients recently exposed to
53 medications such as cefoperazone, disulfiram, or metronidazole.

54
55 Some patients may also have an adverse reaction from swallowing ondansetron oral solution. These may include the
56 following:

57
58 Central nervous system: Headache (oral: 9% to 27%; IV: 17%), fatigue (oral: ≤9% to 13%), malaise (oral: ≤9% to 13%)

59
60 Gastrointestinal: Constipation (6% to 11%)

61
62 1% to 10%:

63
64 Central nervous system: dizziness (7%), agitation (oral: ≤6%), anxiety (oral: ≤6%)

65
66 Dermatologic: Pruritus (2% to 5%), skin rash (1%)

67
68 Gastrointestinal: Diarrhea (oral: 6% to 7%)

69
70 Genitourinary: Gynecologic disease (oral: 7%), urinary retention (oral: 5%)

71
72 Hepatic: Increased serum ALT (>2 times ULN: 1% to 5%; transient), increased serum AST (>2 times ULN: 1% to 5%;
73 transient)

74
75 Local: Injection site reaction (IV: 4%; includes burning sensation at injection site, erythema at injection site, injection site
76 pain)

77
78 Respiratory: Hypoxia (oral: 9%)

79
80 Miscellaneous: Fever (2% to 8%)

81
82 **8.2 Potential Benefits.** Shortened time to relief of nausea and/or vomiting may be a benefit to the two groups allocated
83 to inhaled isopropyl alcohol. The group not receiving inhaled isopropyl alcohol will receive oral ondansetron which has
84 been shown to improve nausea in previous studies (though nausea relief is commensurate to that of intravenous fluids
85 alone). Therefore, we anticipate that all study groups will receive some benefit from the study.

37 **9.0 ADVERSE EVENTS, UNANTICIPATED PROBLEMS, AND DEVIATIONS**
38

39 **9.1** Hines et al found no adverse effects of inhaled ISO in their November 2012 Cochrane review.⁴ An allergy to
40 isopropyl alcohol which is extremely rare but could be serious. Previous toxicological rat studies of inhaled isopropyl that
41 would reproduce adverse effects in humans are not applicable considering this study's minuscule inhalation.¹⁹ Only 1
42 case of death associated to ISO inhalation was found in the literature review, however the deceased was a child that was
43 also bathed with ISO.¹⁰ The study excludes children and there will be no direct contact of ISO to the subject or
44 investigator.

45
46
47 <1% (Limited to important or life-threatening): Abdominal pain, accommodation disturbance, atrial fibrillation,
48 cardiorespiratory arrest (IV), depression of ST segment on ECG, dyspnea, extrapyramidal reaction (IV), flushing, hepatic
49 failure (when used with other hepatotoxic medications), hiccups, hypersensitivity reaction, hypokalemia, hypotension,
50 laryngospasm (IV), liver enzyme disorder, mucosal tissue reaction, myocardial infarction, neuroleptic malignant syndrome,
51 positive lymphocyte transformation test, prolonged Q-T interval on ECG (dose dependent), second-degree atrioventricular
52 block, serotonin syndrome, shock (IV), Stevens-Johnson syndrome, supraventricular tachycardia, syncope, tachycardia,
53 tonic-clonic seizures, torsades de pointes, transient blindness (lasted ≤ 48 hours), transient blurred vision (following
54 infusion), vascular occlusive events, ventricular premature contractions, ventricular tachycardia, weakness
55

56 Adverse events will be recorded on the data collection form, and required Brooke Army Medical Center Institutional
57 Review Board Tracking Log for Adverse Events, Serious Adverse Events & UPIRSOs / UADE
58 Internal Report Log (P52I) and the subject will be clinically managed in the ED.
59

60 **9.2 Reporting Unanticipated Problems Involving Risks to Subjects or Others, Serious Adverse Events and Deaths to**
61 **the RHC-C IRB Office.**
62

63 All unanticipated problems involving risk to subjects or others, unexpected serious adverse events, and all subject deaths
64 related or possibly related to the study will be reported promptly providing initial notification of the event as quickly as
65 possible after the research team's knowledge of the event, but within five (5) business days of identification by [contact]), by e-mail ([contact]), by [contact]) or via
67 letter addressed to IRB Administrator, Regional Health Command-Central Office of the Institutional Review Board, Brooke
68 Army Medical Center, Attn: MCHE-ZQ, Department of Quality and Safety, [name],
69 [name]. A complete written report will follow the initial notification within 10 working days.
70

71 **9.3 Research Monitor.** The research monitor will review all unanticipated problems involving risk to subjects or others,
72 serious adverse events and all subject deaths associated with the protocol and provide an unbiased written report of the
73 event to the RHC-C IRB. Other responsibilities may be assigned by the IRB. The research monitor will comment on the
74 outcomes of the event or problem and in the case of a serious adverse event or death comment on the relationship to
75 participation in the study. The research monitor will also indicate whether he/she concurs with the details of the report
76 provided by the study investigator. Reports for events determined by either the investigator or research monitor to be
77 possibly or definitely related to participation and reports of events resulting in death will be promptly forwarded to the
78 RHC-C IRB office.
79
80

81 **10.0 WITHDRAWAL FROM STUDY PARTICIPATION.** Patients may withdraw their consent at any time and
82 discontinue further participation in this study without affecting their eligibility for care or any other benefits to
83 which they are entitled. They may withdraw for any reason. Should they choose to withdraw, they must notify
84 the principle investigator or any other member of the research team. They may do this during the study in
85 person by verbally stating to the research team member that they wish to withdraw. After the study, they may
86 withdraw by calling or writing the principle investigator (PI contact information provided to all study participants
87 on the informed consent document). We will analyze any data collected on these patients prior to withdrawal unless
88 requested by the subject to destroy their data form. There are no risks associated with withdrawing from the study.
89

90 **11.0 USAMRMC Volunteer Registry Database.** N/A
91

92 **12.0 REFERENCES.**

5. Pellegrini J, et al. Comparison of inhalation of isopropyl alcohol vs promethazine in the treatment of postoperative nausea and vomiting (PONV) in patients identified as at high risk for developing PONV. *AANA J* 2009;77:293-9.
6. Winston AW, et al. Comparison of inhaled isopropyl alcohol and intravenous ondansetron for treatment of postoperative nausea. *AANA J* 2003; 71:127-32.
